6.0 SOCIAL HARMS

Because of the purely behavioral nature of the intervention, no "biological" adverse experiences directly attributable to the intervention are anticipated. As such, no adverse events will be reported to the DAIDS SAE Office. Such events have not been identified in the SHIELD study in Baltimore, nor in the NIDA-funded cohort study of injection drug users conducted by Johns Hopkins University and Research Institute for Health Sciences of Chiang Mai of Chiang Mai (RIHES) in Thailand.

However, given the illegal status of drug use, the social stigma that surrounds injection drug use and perceptions of drug users held by many members of the communities in which the study will be conducted, there are potential social harms that could occur purely as a result of participation in a study targeting injection drug users. These could include discriminatory treatment and violence associated with possible disclosure of participants' drug or sex-related behaviors or of their HIV serostatus.

In Philadelphia, all activities involving participants will be conducted in venues that mask the criteria for study participation. It is impossible and unwise to think that the primary purpose of the study can be kept secret (i.e., a prevention study for IDUs) from the community, including the police. An appropriate working relationship with the local law enforcement agency, which recognizes the urgent need to prevent HIV in this population, has been established. Such relationships have assisted our outreach staff whose presence in the community is understood and respected. Site staffs do not disclose the names of participants to anyone other than members of the field research staff meetings on topics of recruitment and follow-up. All interview and laboratory data are securely stored in a confidential manner with no identifying information other than study number. All identifying information is stored in a separate and secure area and does not include study numbers. All computerized information is password-protected and encrypted when saved. Over the past 13 years, this site has enrolled and followed over 3000 IDUs without any instances of police intrusion or unwanted disclosure of personal information of any type.

Since 1999, the Chiang Mai site has enrolled almost 1,000 IDUs and has followed 400 IDUs of different ethnic groups from varying geographic areas in northern Thailand. The site team has established good relationships with drug users, communities, non-governmental organizations (NGOs), and governmental organizations, including law enforcement agencies, throughout the years. The research team includes staff from a regional drug-dependence treatment and rehabilitation center of the Thailand Ministry of Public Health. Researchers from RIHES, under the auspices of the Thailand Ministry of University Affairs, serve as interviewers and counselors from the communities, including hill tribe groups. Information on participants obtained from interviews in the form of paper questionnaires and laboratory tests are stored in separate and secure filing cabinets without any personal identifiers except numeric study numbers. All computerized information is password-protected and encrypted. The Chiang Mai site has never experienced any intrusion, harassment, or information request from law enforcement agencies or communities regarding identities of any participant IDUs. However, this site is not protected by a Certificate of Confidentiality, which is not recognized by the laws governing Thailand. However, all cognizant public agencies are fully briefed about the site's work and the importance of protecting the confidentiality and identity of all research participants. In 10 years of conducting HIV research in marginalized populations in Thailand, there have been no negative experiences in this regard.

Additional information about protections against social harms can be found in Section 8.5.

6.1 Monitoring of Social Harms

In order to prevent against adverse social events, "social harms" will be monitored closely throughout the study. At each follow-up visit, a series of structured questions will be used to probe for interpersonal, legal, housing and healthcare problems that have occurred as a result of study participation. All subjects will also be reminded of the importance of reporting problems to study staff between regularly scheduled visits and instructed on how to contact study staff should problems occur during intervals between visits. When problems are identified, additional data regarding the severity and resolution will be described and recorded on a separate reporting form and will include a description of actions taken by the participant, the site staff, and others to resolve or respond to the problem. The nature and frequency of these social impact reports will be monitored by the protocol team as they occur. In addition, these data will be routinely reviewed by the DAIDS Prevention Data and Safety Monitoring Board (DSMB).

7.0 STATISTICAL CONSIDERATIONS

7.1 General Design

This is a phase III, multi-site, two-arm, randomized, controlled study of a network-oriented peereducation training intervention for prevention of HIV infection through reduction of HIV risk behaviors among HIV-uninfected IDUs and members of their HIV risk networks. All participants in the study will receive enhanced HIV counseling and testing at screening and semiannually during follow-up. Indexes in the intervention arm receive a six-session peer education training intervention, plus a booster session at six and 12 months, with a maximum of 12 indexes. Indexes in the control arm receive no additional training. Primary and secondary endpoints will be measured on each participant - indexes and network members - every six months for a maximum of 30 months.

7.2 Study Endpoints

7.2.1 Primary Endpoint

Incident HIV-1 infection in IDU peer networks (indexes and network members) as determined by the seroconversion algorithm in Appendix I.

7.2.2 Secondary Endpoints– Self reported HIV Risk Behaviors

Self- reported HIV risk behaviors for indexes and network members, as follows:

- Frequency of injection drug use
- Frequency of sharing of injection equipment (needles, cookers, cotton, and rinse water)
- Number of people injection equipment shared with
- Frequency of properly disinfecting injection equipment
- Entering into drug treatment
- Cessation of injection drug use
- Number of sex partners
- Frequency of condom use during sex

7.2.3 Secondary Endpoints – Community Norms

- Self-reported behaviors: Network norms will be measured by aggregating the self-reports within networks of the HIV risk behaviors listed above
- Psychometric measures of perceived network group social norms
- Self-reports of frequency of peer discussions of risk behaviors
- Self-reports of frequency of encouragement by network members to reduce HIV risk
- Perception of peer risk behaviors

7.2.4 Potential Effect Modifiers, Confounders and Covariates

7.2.4.1 Individual Risk Factors

- Alcohol use
- Demographics
- Non injection drug use

7.2.4.2 Network Risk Factors

- Network size
- Change in network composition
- Marker of exposure to intervention (tag phrase to measure contamination across arms)

7.3 Sample Size and Accrual

Sample size estimates are based on a group, randomized design, where all members of a network are randomized to the same arm. The sample size required with a group-randomized design is increased depending on the strength of correlation between outcomes within a network, relative to an individually randomized design.

Sample size computations use the formulation given by Donner et al^{32} , where the total number of participants per arm required in a design with clusters of size *n* is given as:

$$T = \frac{(Z_{\alpha} + Z_{\beta})^{2} (P_{E}(1 - P_{E}) + P_{C}(1 - P_{C}))(1 + (n - 1)\kappa)}{(P_{E} - P_{C})^{2}}$$

where Z_{α} , Z_{β} are standardized Normal quantiles for type I error α and power $1 - \beta$, P_E and P_C are, respectively, the cumulative probability of seroconversion in the experimental and control arms, and κ is analogous to an intraclass correlation coefficient. The number of networks required per arm is then $\frac{T}{n}$.

 κ can be expressed as:

$$\kappa = \frac{P_1^* + P_0^* - (P^n + (1 - P)^n)}{1 - (P^n + (1 - P)^n)}$$

where P_1^* and P_0^* are the probabilities of network concordance, i.e. the probability all and none of the members of network seroconvert, respectively. The numerator of κ measures the difference between the actual concordance among clusters and the expected concordance rate under the assumption of independence, i.e. κ measures how much agreement exists in a cluster beyond the amount expected by chance.

7.3.1 Power for seroincidence endpoints

Philadelphia has established a seroincidence rate of 2 per 100 person-years and the current rate established in Thailand among IDU is 10.4 per 100 person-years, although in the sample size computations a conservative 8% rate is used. One-third of the networks will enroll in Philadelphia and two-thirds in Thailand.

Sample size computations are made using the following assumptions:

- Mean seroincidence rate: 6% per year for pooled sites, 8% per year for the Thai sites.
- Loss to follow up 10% per year
- 30 months recruitment, minimum 18 months follow up, maximum 30 months
- 90% power, 5% Type I error

The formula above is used, substituting for P_E and P_C estimates \overline{P}_E and \overline{P}_C , the average probability of seroconverting during the study on the experimental and control arms. These estimates take loss to follow-up and differential length of follow-up into account.

Rate	Effect	\overline{P}_{F}	\overline{P}_{c}	K	Total/	Networks/	Total/	Networks/	Total/	Networks/
		L	C		arm	arm	arm	arm	arm	arm
					Mean pe	er network $= 4$	Mean pe	er network $= 3$	Mean pe	er network $= 2.5$
6%	33%	7.8%	11.6%	0.1	1671	418	1542	515	1478	592
				0.2	2057	515	1800	600	1671	669
				0.3	2442	611	2057	686	1864	746
6%	40%	7.1%	11.6%	0.1	1112	278	1026	343	983	394
				0.2	1368	343	1197	400	1112	445
				0.3	1625	407	1368	457	1240	496
8%	33%	10.4%	15.3%	0.1	1246	312	1150	384	1102	441
				0.2	1534	384	1342	448	1246	499
				0.3	1821	456	1534	512	1390	556
8%	40%	9.4%	15.3%	0.1	828	208	765	255	733	294
				0.2	1020	255	892	298	828	332
				0.3	1211	303	1020	340	924	370

 Table 1: Sample size requirements for two-arm group randomized network study

The sample size has been chosen to achieve 90% power to detect a 40% reduction in rate of infection, from 6% per year to 3.6% per year. This requires 445 networks per arm, followed for an average of 27 months (minimum of 18 month, maximum of 30 months), with a seroincidence evaluation of an average of 2.5 HIV-uninfected people per network (HIV-uninfected peer leader and one or more network members, HIV-uninfected at enrollment) and loss to follow-up of 10% per year, using two-sided alpha of 0.05 and intraclass correlation of 0.2. To achieve the same power to detect a 33% reduction, from 6% to 4%, requires 669 networks per arm.

Enrolling 445 networks per arm implies a study enrollment of approximately 2,250 HIVuninfected participants: approximately 150 networks per arm in Philadelphia (750 HIVuninfected participants) and 300 networks per arm in Thailand (1500 HIV-uninfected participants). The protocol allows for the enrollment of HIV-infected network members, and assuming a prevalence of 20% and 30% amongst injectors in Philadelphia and Thailand respectively, we are projecting enrollment of 90 HIV-infected network members in Philadelphia and 270 in Thailand. The total participant enrollment, including both HIVinfected and HIV-uninfected participants, is thus projected to be 2610: 1770 in Thailand and 840 in Philadelphia, with an average of 1.9 network members per index participant. Network members who are infected with HIV will be excluded from the analysis of the primary endpoint.

For the endpoint at the Thailand site alone, assuming a higher seroincidence of 8% per year, 90% power to detect a 40% reduction in seroincidence is achieved with 332 networks per arm.

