3.5 Enrollment of Networks and Randomization

Prospective index participants in networks consisting of one or more eligible network members (either HIV-negative or positive) will be contacted within 60 days of their HIV pre-test counseling visit to learn of their eligibility status. All individuals to be randomized must have initiated screening procedures fewer than 60 days prior to the planned date of randomization. Individuals who exceed this 60-day limit may be re-screened, and all screening procedures must then be completed before their network is qualified for randomization. Index participants will be randomized along with their network member(s) to either the experimental or control arm. Study staff will contact index participants and network members to confirm their enrollment status.

If no prospective network members identified by an index have presented for screening, been found to be eligible, and provided study consent within the 60 days following the index participant's pre-test counseling visit, the index participant will be considered ineligible for the study as a member of that network.

Note: Individuals who initially screen (and provide consent) as an index member may subsequently be screened as a network member for another network, but must first complete the network member informed consent process and member screening assessment. As above, if the time between the participants initial HIV blood draw and enrollment/randomization of the network exceed 60 days, screening procedures as specified in the SSP manual must be repeated.

Note: Individuals who initially screen as a network member may subsequently be screened as a network member for another network, but must first complete the member screening assessment for each network they are screening for. As above, if the time between the participants' initial HIV blood draw and enrollment/randomization of the network for which they qualify exceed 60 days, screening procedures as specified in the SSP manual must be repeated.

Note: Individuals who initially screen as a network member may not screen as an index member for 3 months after their initial blood draw for HIV testing to allow for the dissipation of any

measurement effects. After this three-month period, the individual may undergo the screening procedures as an index member after completing the index screening informed consent process.

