7.3.2 Power for Behavioral Endpoints

One third of the networks will be enrolled in Philadelphia, approximately 150 networks per arm; the remainder will be enrolled in Thailand, approximately 300 per arm. Due to the lower seroincidence in the Philadelphia site, it will not be possible to assess the effect of the intervention at that site using primary outcome information. Differences in secondary outcomes of self-reported behavioral outcomes will be assessed to evaluate the intervention at the Philadelphia site (as well as in Thailand).

For behavioral endpoints, assuming repeated measurement at each visit and a conservative average of 12 visits per network [average number of visits per participant = 5, average number of members = 2.9, loss to follow-up/year = 10%], the formula above can be used to estimate the power for change of behavior within the networks. P_{Exp} and $P_{Control}$ are the

probabilities of a behavior in the previous six-month period. As shown in Table 2 below, there is adequate power to detect 10% behavioral change among networks at the Philadelphia site, depending upon the prevalence in the control arm and the correlation within networks.

			Networks/arm				
P_{Exp}	$P_{Control}$	К	Power: 80%	Power: 90%			
40	50	0.1	68	91			
		0.2	103	138			
		0.3	138	185			
30	40	0.1	62	83			
		0.2	95	127			
		0.3	127	170			
20	30	0.1	51	69			
		0.2	78	104			
		0.3	105	140			
10	20	0.1	35	46			
		0.2	53	71			
		0.3	71	95			

 Table 2: For network aggregates: Sample size requirements for testing proportions with repeated measurements: cluster size=12

Similarly, for testing behavioral change amongst the network indexes, sample size estimates have been computed for repeated measures from the five visits of the index participant. Table 3 shows adequate power at the Philadelphia site for detecting 15% behavioral change in the networks depending on the correlation within networks and the prevalence in the control arm.

			Networks/arm	
P Experimental	P Control	К	Power: 80%	Power: 90%
35	50	0.1	47	63
		0.2	60	81
		0.3	74	99
25	40	0.1	42	56
		0.2	54	72
		0.3	66	88
15	30	0.1	24	45
		0.2	33	57
		0.3	43	70
10	20	0.1	55	74
		0.2	71	95
		0.3	87	116

 Table 3: For network indexes: Sample size requirements for testing proportions with repeated measurements: cluster size=5

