7.6 Interim Monitoring Process

The duration of the study will be approximately 4 years. It is estimated that the enrollment period will be approximately 30 months. Study conduct will be monitored regularly by the HPTN Study Monitoring Committee (SMC) with a focus on issues relating to quality of study conduct, such as overall and site-specific rates of recruitment, adherence to study interventions and visit schedules, and retention. The sample size may be adjusted after 12 months if it is apparent that the mean number of HIV-uninfected network members enrolled is insufficient to achieve adequate power.

The study will also be monitored by the DSMB. Administrative data will be reviewed every 6 months during the first 18 months of the study. Primary and secondary endpoint data will be monitored annually. Sequential monitoring methods will be used to develop boundary guidelines for early termination.

The randomization code will be maintained by the research biostatistician at the HPTN Statistical and Data Management Center. At each interim efficacy analysis, the chairman of the DSMB will be given a sealed envelope with the randomization code enclosed. The DSMB will be encouraged to conduct unblinded reviews of efficacy data.

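### The 445 networks per arm for 90% power rest on a formula for networks of one fixed size; evaluable network size must vary, so the stated power is somewhat too high, and the 12-month review names only the mean size

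*Protocol*

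**What the plan says.** Section 7.3 gives the "total number of participants per arm required in a design with clusters of size" n. Its design effect is 1+(n−1)κ, with no term for spread in n. Section 7.3.1 puts mean sizes of 4, 3 and 2.5 in place of n in Table 1 and chooses the sample size for "90% power to detect a 40% reduction in rate of infection, from 6% per year to 3.6% per year". The result is 445 networks per arm, "with a seroincidence evaluation of an average of 2.5 HIV-uninfected people per network", with "loss to follow-up of 10% per year, using two-sided alpha of 0.05 and intraclass correlation of 0.2". A parenthesis there describes the people counted as an uninfected index plus at least one member who is uninfected at enrollment.

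Other sections fix how network size arises:

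- Section 3.5 accepts "networks consisting of one or more eligible network members (either HIV-negative or positive"). Section 5.2 likewise asks for an index and at least one member, and no maximum is stated.
- Section 7.3.1 excludes HIV-infected members from the primary analysis.
- Section 3.4 expects on average 1.5 uninfected and 0.4 infected members per index.

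On review, Section 7.6 says: "The sample size may be adjusted after 12 months if it is apparent that the mean number of HIV-uninfected network members enrolled is insufficient" for adequate power. Section 2.3 separately provides for a sample size adjustment if the number of infected members threatens the ability to detect an effect. Section 7.3.4 adds monitoring of seroincidence and of the average number of members. Section 7.3.2 uses the same formula for behavioral endpoints ("For network aggregates: Sample size requirements for testing proportions with repeated measurements: cluster size=12").

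**The concern.** No network can contain 2.5 people, so variation in size is certain. For an analysis that gives each person equal weight, such as the marginal Cox model of Section 7.5.1, large networks add more correlated information than the mean suggests. The design effect then depends on the size-weighted mean, which exceeds the simple mean whenever sizes differ. The direction of the error is known from the protocol alone; its size is not, because no variance is given.

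Two things are at stake. The headline power is a little optimistic. And a review that compares the mean number of uninfected members with its target of 1.5 could report that all is well while the effective sample is a few percent short.

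There is also an inconsistency of wording. Under Section 3.5 an index whose only member is HIV-infected forms an eligible network and contributes one person to the primary analysis. Read as a statement about every network, the parenthesis in Section 7.3.1 rules that network out.

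**Working it through.** **Inputs from the protocol.** Two-sided alpha 0.05 and power 90%, so Zα+Zβ = 1.960+1.282 = 3.2415. Table 1, 6% rate and 40% effect: P_E = 7.1%, P_C = 11.6%. κ = 0.2. Mean evaluable size 2.5.

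**Reproducing 445.** T = (Zα+Zβ)² × [P_E(1−P_E)+P_C(1−P_C)] × [1+(n−1)κ] / (P_E−P_C)².

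- Design effect: 1+(2.5−1)×0.2 = 1.30.
- With the rounded probabilities: 10.507×0.16850×1.30/0.002025 = 1137, or 455 networks.
- With less rounding (annual risks converted to hazards, 10% annual loss as a competing hazard, 27 months): P_E = 7.06%, P_C = 11.60%, T = 1114, or 446 networks.

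The protocol states 1112 and 445. Table 1 is therefore the fixed-size formula with a mean put in for n.

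**Unequal sizes.** Replace n by Σn²/Σn = mean + variance/mean. With variance v:

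Design effect = 1+(2.5+v/2.5−1)×0.2 = 1.30+0.08v.

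Power at 445 networks = Φ(3.2415×√(1.30/DE) − 1.960). At 450 networks the term under the root is multiplied by 450/445. Networks needed for 90% = 445×DE/1.30.

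All values of v are assumptions except the lower limit. With whole-number sizes and mean 2.5, the smallest variance is 0.25 (half the networks of size 2, half of size 3).

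| Variance v | Design effect | Power at 445 | Power at 450 | Networks for 90% |
|---|---|---|---|---|
| 0 (protocol) | 1.300 | 90.0% | 90.3% | 445 |
| 0.25 (minimum) | 1.320 | 89.6% | 89.9% | 452 |
| 0.8 | 1.364 | 88.6% | 88.9% | 467 |
| 1.5 (index plus Poisson number of members) | 1.420 | 87.3% | 87.7% | 486 |
| 2.0 | 1.460 | 86.4% | 86.8% | 500 |

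The loss of effective sample is 1−1.30/DE: 1.5%, 4.7%, 8.5% and 11.0% for the four variances above zero. Simulated clustered outcomes with cluster-robust tests (6,000 runs each) gave 89.7%, 88.7% and 88.2% for the first three. With efficient weighting, the Poisson case gives 88.4% in place of 87.3%.

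**Networks with no uninfected member.** Take an illustrative distribution of 1, 2, 3 and 4 members in 40%, 35%, 20% and 5% of networks (mean 1.9, as in Section 7.3.1). The projected infected fractions are 90/(90+450) = 16.7% in Philadelphia and 270/(270+900) = 23.1% in Thailand. If infection is independent between members, the share with none uninfected is 0.40q+0.35q²+0.20q³+0.05q⁴, or 7.7% at q = 0.167 and 11.4% at q = 0.231: about 8% to 11%. The variance of evaluable size in this example is about 0.8.

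**Table 2.** For 40% against 50%, the design effect becomes 1+(12(1+CV²)−1)κ. At an assumed CV² of 0.164 and κ = 0.3, the need for 80% power rises from 138 to 157 networks per arm, and Philadelphia's 150 give about 78%. The need reaches 150 at a CV² of about 0.106, so below roughly 0.10 this cell keeps 80%.

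**The case against.** The strongest reply is about size. The only loss that the protocol forces is 0.4 points, and at the planned 450 networks power is still 89.9%. Rounding the two probabilities to Table 1's printed digits moves the answer further, from 445 to 455. Everything beyond the minimum rests on an assumed variance. Table 1 already shows 394, 445 and 496 networks for κ of 0.1, 0.2 and 0.3, which at 445 networks means about 93%, 90% and 86.7% power. Uncertainty in κ matters at least as much as spread in size, and only the variance of 2.0 goes beyond that span. Efficient weighting softens the loss, and Section 3.1.1 asks each index to try to recruit at least two members. All of this stands and limits the point to a modest correction. It does not remove the bias, which has one direction for any κ above zero and adds to whatever κ turns out to be.

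A reader might infer that the mean is the protocol's only guard on power. It is not: the adjustment in Section 2.3 is triggered by loss of ability to detect an effect, and Section 7.3.4 monitors seroincidence. Neither mentions spread in network size, however, and Section 7.6 names only the mean.

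A reader might also infer that Table 1 is miscalculated. It reproduces, and its columns are openly labelled as means; the fault is in the choice of formula. The parenthesis in Section 7.3.1 can be read as saying only who is counted, in which case it needs clearer wording and no more.

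**Conclusion.** The point holds at modest size. At κ = 0.2 with equal weight per person, power at 445 to 450 networks per arm is about 87% to 90% for size variances from 0.25 to 1.5, and 86% to 87% at 2.0. The direction follows from the protocol; the amount beyond 0.4 points depends on a variance that it does not give.

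Three stronger readings are not supported. The trial is not shown to be seriously underpowered or to need more networks. The share of networks without an uninfected member should not be computed from the 20% and 30% prevalences: applied to 1.9 members, 30% would leave only 1.33 uninfected members, not the planned 1.5. The protocol's projected infected fractions give about 8% to 11%, and that is itself illustrative. And Philadelphia's behavioral power does not fail as a whole: the Table 2 effect highlighted here is one κ = 0.3 cell, it depends on an assumed CV² above about 0.10, and Section 7.3.2 already makes adequacy conditional on prevalence and correlation.

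**What to change.** - **Section 7.3:** replace 1+(n−1)κ by 1+(Σn²/Σn−1)κ, where n is the number of HIV-uninfected people in each network.
- **Section 7.3.1:** state the assumed range of size variance and give power at 445 to 450 networks per arm as about 87% to 90% over that range, without enrolling more. Reconcile the parenthesis with Section 3.5 so that it is clear a network may contribute the index alone.
- **Section 7.6:** base the 12-month review on Σn²/Σn of HIV-uninfected people, pooled over arms, together with the mean.
- **Table 2:** add a note that its figures assume an equal number of observations per network.

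The cost is protocol wording and a slightly less favorable stated power. It needs no added participants or procedures, since network membership and HIV status at enrollment are already recorded.

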7.5 Analysis Plan

7.5.1 Primary Analysis

HIV seroincidence

Comparison of HIV seroincidence in the two arms will be based on the decrease in risk of infection between the two arms estimated via proportional hazards regression, stratified by site. Statistical estimation and inference will be based on the marginal models approach to extending the Cox model to the analysis of correlated survival data, described for example in Therneau. This has much in common with the Generalized Estimating Equation (GEE) approach of Zeger, et al.36

HIV seroincidence in Thailand

The comparison of seroincidence rates between arms will be repeated for the Thailand site alone.

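### The only power quoted for the Thailand-alone comparison belongs to 332 networks per arm; the planned 300 per arm gives about 86–87%, which the protocol never states

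*Protocol*

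**What the plan says.** Section 7.3.1 sets the operating characteristics once for both calculations: "90% power, 5% Type I error". It gives the control rates as "Mean seroincidence rate: 6% per year for pooled sites, 8% per year for the Thai sites". The trial's size is then fixed on the pooled comparison: 445 networks per arm for a 40% reduction from 6% per year, with 2.5 HIV-uninfected people per network, "using two-sided alpha of 0.05 and intraclass correlation of 0.2".

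For Thailand alone, the same section says that "90% power to detect a 40% reduction in seroincidence is achieved with 332 networks per arm". The paragraph just before that sentence splits enrolment by site and plans "300 networks per arm in Thailand (1500 HIV-uninfected participants". The same Thai number appears as 600 networks in total in the Protocol Summary and Section 3.4, and as about 300 per arm in Section 7.3.2.

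Section 7.5.1, headed Primary Analysis, describes the pooled site-stratified Cox comparison and then adds: "The comparison of seroincidence rates between arms will be repeated for the Thailand site alone".

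**The concern.** The Thailand-alone comparison has one power figure in the protocol, and it is tied to a number of networks that the protocol does not plan to enrol. A reader who meets that sentence straight after the enrolment plan will probably take 90% as the power of the Thai analysis.

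This matters more than it would for an ordinary subgroup. Section 7.3.2 says that the effect in Philadelphia cannot be assessed on the primary outcome because incidence there is too low. Thailand is therefore the only site where HIV incidence can be tested separately, and a null Thai result would be interpreted against its stated power.

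A lesser question arises from the layout of Section 7.5.1. Two comparisons stand under one Primary Analysis heading, with no statement of how the second relates to the first.

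**Working it through.** **Inputs (all from Section 7.3 and Table 1)**

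- Two-sided alpha 0.05 and power 0.90, so the quantiles are 1.960 and 1.2816, which sum to 3.2415.
- Average seroconversion probabilities for the 8% rate and 40% effect: 9.4% experimental, 15.3% control. Of these the protocol says: "These estimates take loss to follow-up and differential length of follow-up into account". No further allowance for dropout is due.
- Cluster size 2.5. The Thai plan agrees with it: 1500 / 600 = 2.5.
- Design kappa 0.2, with 0.1 and 0.3 as the Table 1 alternatives.
- Required networks per arm in Table 1 (8%, 40%, mean 2.5): 294, 332 and 370 at kappa 0.1, 0.2 and 0.3.
- Planned Thai networks per arm: 300.

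**Step 1. Reproduce 332.** The protocol's formula is

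T = (Zα + Zβ)² × [PE(1−PE) + PC(1−PC)] × [1 + (n−1)κ] / (PE−PC)²

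- Variance term: 0.094 × 0.906 + 0.153 × 0.847 = 0.2148
- Design effect: 1 + 1.5 × 0.2 = 1.3
- T = 3.2415² × 0.2148 × 1.3 / 0.059² = 843 per arm
- Networks = 843 / 2.5 = 337.1

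This is within 1.5% of 332. With PC = 0.1535, inside the rounding of 15.3%, the result is 332.0. The protocol's figure is sound.

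**Step 2. Size of the gap.** 332 − 300 = 32 networks per arm, and 32 / 332 = 9.6%.

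**Step 3. Power at 300.** With M the number of networks per arm that gives 90% power, the same formula inverts to

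Power = Φ(3.2415 × √(300 / M) − 1.960)

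| κ | M (Table 1) | Power scaled from Table 1 | Power from printed 9.4% and 15.3% |
|---|---|---|---|
| 0.1 | 294 | 90.6% | 90.2% |
| 0.2 | 332 | 86.9% | 86.4% |
| 0.3 | 370 | 83.1% | 82.5% |

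At κ = 0.2 the scaled figure is Φ(3.2415 × √(300/332) − 1.960) = Φ(1.121) = 86.9%. Letting both printed probabilities vary within their rounding gives 85.2% to 87.5%. Taking exactly two-thirds of 445 (297 networks) gives 86.0%.

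**Step 4. The two comparisons under Primary Analysis.** Suppose, which the protocol does not say, that either test at 5% could alone count as success. Assume also that events fall in proportion to networks times incidence, with 8% in Thailand and 2% in Philadelphia. Thailand's share is then 2 × 8 / (2 × 8 + 1 × 2) = 0.889. The two statistics correlate at √0.889 = 0.943, and the bivariate normal chance of at least one false positive is 6.6%. If the tests were independent it would be 1 − 0.95² = 9.75%, but the Thai data are most of the pooled data.

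**The case against.** The strongest reply is that no false figure is printed. The sentence states what 90% power would require; it does not say that 300 networks deliver it, and the 300 stands in plain view one paragraph earlier. The trial was sized on the pooled comparison, which needs 445 networks per arm against about 450 planned, and nothing commits the design to 90% in Thailand. All of this stands. A reader might infer that the protocol claims 90% power at 300, or that the trial as a whole is undersized; the text supports neither.

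It can also be said that 8% is cautious, because Section 7.3.1 cites a current Thai rate of 10.4 per 100 person-years. Assuming exponential infection times and uniform accrual, that rate would give about 91% at 300 networks. The cushion cannot be relied on: 8% is the planning value, and Section 3.3 reports 7.89 per 100 person-years in the Thai cohort. The sample-size review in Sections 7.3.4 and 7.6 responds to seroincidence and network size, and does not address this gap.

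On error control, a reader might infer that two primary tests at 5% give two chances of success, so that the 5% is not kept. The documents do not support that. The primary objective (2.1) and primary endpoint (7.2.1) are not site-specific. Section 2.3 rests the inference on the overall site-adjusted relative risk and says that single-site results do not generalize convincingly. Section 7.3.1 sizes the trial on the pooled test. Nothing says that a Thailand-only result would count as success, and an analysis plan not at hand may rank the two comparisons. What remains is only that the heading in Section 7.5.1 covers both without saying which decides.

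**Conclusion.** The point holds as a mismatch of planning figures. The only size-and-power pair given for the Thailand-alone comparison, 332 networks per arm for 90%, is not what the plan delivers. At the planned 300 per arm and the design kappa of 0.2, power is about 86–87%. It reaches 90% only if kappa is nearer 0.1, and falls to about 83% at 0.3. These figures rest on the protocol's own formula, its 8% control rate, a 40% reduction and 2.5 uninfected people per network.

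The shortfall is modest and the pooled primary test is untouched. The sentence should still be corrected, because it concerns a comparison listed under Primary Analysis at the only site that can be tested separately on HIV incidence.

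The relation between the two comparisons is a minor matter of wording. The 6.6% is conditional on a success rule that the protocol does not state and on the assumed 89% Thai share of events. It is not evidence that the 5% error rate is breached.

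**What to change.** In Section 7.3.1, replace the Thailand-alone sentence with: *With the planned 300 networks per arm in Thailand, power to detect a 40% reduction is about 86–87% (kappa 0.2); 90% would require 332 per arm.* The values at kappa 0.1 (about 90%) and 0.3 (about 83%) could be added in the same line.

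In Section 7.5.1, add one sentence naming the pooled site-stratified Cox comparison as the primary test and the Thailand-alone comparison as supportive. Testing Thailand at 5% only if the pooled result is significant would serve equally well. Either agrees with Sections 2.3 and 7.3.1.

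The cost is two sentences of protocol text. There are no extra participants, visits or data, and the sample size does not change; the only concession is a slightly lower stated power for Thailand.
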